#### PK parameters and immunogenicity status

The following analyses will include patients in both the immunogenicity analysis set and in the PK parameter analysis set. The PK endpoints pertinent to the immunogenicity analyses are  $C_{\text{trough}}$  and  $C_{\text{max}}$ . Blood samples for avelumab, utomilumab, PF-04518600, and PD 0360324 PK will be collected as outlined in the “Schedule for Pharmacokinetic Sample Collection” table of the Schedule of Assessments section of the protocol.

$C_{\text{trough}}$  and  $C_{\text{max}}$  will be summarized descriptively (n, mean, SD, CV, median, minimum, maximum, geometric mean, its associated CV, and 95% CI) by nominal time and ADA status. Linear-linear plots of mean and median for  $C_{\text{trough}}$  and  $C_{\text{max}}$  over nominal time and by ADA status will be presented.

Among patients with treatment-induced ADA, analyses will be conducted to assess whether  $C_{\text{trough}}$  and  $C_{\text{max}}$  have any changes before and after the first positive ADA assessment. To be included in this analysis, patients must have the same PK parameter available both before and after the first positive ADA assessment. Relative PK day will be calculated as:

$$(\text{PK assessment nominal day}) - (\text{first positive ADA assessment nominal day}).$$

Nominal day is the protocol scheduled timing for an assessment. For example, if  $C_{\text{trough}}$  is collected on Day 1 of Cycle 2 and the first positive ADA result is observed on Day 1 of Cycle 3, then the relative PK day for this  $C_{\text{trough}}$  is -28. Linear-linear plots of mean and median for  $C_{\text{trough}}$  and  $C_{\text{max}}$  over relative PK day will be presented.

CCI

CCI

CCI

### 6.4. Subset Analyses

ORR and DR (if meaningful) will be summarized in the following subsets within each treatment group:

- general prior anti-cancer immuno-therapy (Yes, No)
- Checkpoint inhibitors
  - prior PD-1/PD-L1 therapy (Yes, No)

- prior anti-CTLA4 therapy (Yes, No)
- prior checkpoint inhibitor status (relapsed/resistant, refractory, naïve)
  - naïve: has not previously received a checkpoint inhibitor
  - resistant/relapse: progressed after SD or better
  - refractory: BOR of PD
- HPV status (positive, negative) for SCCHN patients
- PD-L1 status (positive, negative, unknown) at baseline

For CD8, descriptive statistics will be provided by objective response category.

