#### Secondary Objectives

- To assess the overall safety and tolerability of avelumab and other immune modulators when given in combination;
- To characterize the PK of avelumab and other immune modulators when given in combination;
- To evaluate the immunogenicity of avelumab and other immune modulators when given in combination;
- To assess the antitumor activity of avelumab and other immune modulators when given in combination in patients with locally advanced or metastatic solid tumors;
- To assess the correlation of antitumor activity of avelumab and other immune modulators with immune biomarkers in baseline tumor tissue.

CCI

- CCI [REDACTED]  
[REDACTED]  
[REDACTED]  
[REDACTED]
- CCI [REDACTED]  
[REDACTED]

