### 3.2.5. Biomarker endpoints

- Biomarkers such as PD-L1 expression and tumor infiltrating CD8+ T lymphocytes in baseline tumor tissue.

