**Table 3. Biomarker Definition and Determination**

Parameter	Definition	Method of Determination
PD-L1 expression	The percent of counted cells scored as PD-L1+ and qualitative assessment of PD-L1 staining on tumor and inflammatory cells as defined by cell morphology in regions of interest	Pathologist, assisted by image analysis
Tumor infiltrating CD8+ lymphocytes	The percent of counted cells that are scored as CD8+	Pathologist, assisted by image analysis

CCI [REDACTED]

- CCI [REDACTED]  
[REDACTED]  
[REDACTED]  
[REDACTED]  
[REDACTED]

- CCI [REDACTED]

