## 5.2. General Methods

In this study ‘**treatment group**’ refers to one of the cohorts described in Section 3.4.1. Unless otherwise noted the analyses and summaries will be performed as outlined below

**Combinations A and F:** combined Phases 1b and 2 (Cohorts A1, A2, A3 and Cohorts F1, F2 and F3) and the data from Phase 2 (Cohorts A4, A5, A6, A7, A8, A9, A10).

**Combinations B, C and D:** Phase 1b and from Phase 2 separately and for each combination.

Baseline characteristics, disposition and efficacy data will be summarized based on the FAS by treatment group as noted above.

DLTs will be summarized based on the DLT-evaluable set by treatment group from Phase 1b only. Other safety data, exposure data, concomitant medications and non-drug treatments will be summarized based on the safety analysis set by treatment group as noted above.

PK data will be summarized based on the PK analysis set by treatment group as noted above.

Biomarker data will be summarized based on the biomarker analysis sets by treatment group as noted above.

Immunogenicity data will be summarized based on the immunogenicity analysis set by treatment group as noted above.

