#### **6.2.2.1. Tumor shrinkage from baseline**

Tumor shrinkage will be summarized as the percent change from baseline in target lesions (sum of longest diameter for non-nodal lesion and short axis for nodal lesion) per time point. It will be derived as:

- $((\text{Sum of target lesions at week XX} - \text{sum of target lesions at baseline}) / \text{sum of target lesions at baseline}) \times 100$

The maximum reduction in target lesions from baseline will be derived across all the post-baseline assessments until documented disease progression, excluding assessments after start of subsequent anti-cancer therapy, as:

- $\text{Minimum of } ((\text{sum of target lesions at week XX} - \text{sum of target lesions at baseline}) / \text{sum of target lesions at baseline}) \times 100$

A waterfall plot of maximum percent reduction in the sum of longest diameter for non-nodal lesions and short axis for nodal lesions from baseline will be created by treatment group. These plots will display the best percentage change from baseline in the sum of the diameters of all target lesions for each patient with measurable disease at baseline and at least one post-baseline assessment.

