##### **Combinations B, C and D**

The following biomarker analyses will be based on the biomarker analysis sets by treatment group using the data from Phase 1b and from Phase 2 separately and for each combination.

For continuous measurement biomarker results, summary statistics (eg, the mean, standard deviation, median, percent of coefficient of variation, and minimum/maximum levels) will be determined at baseline and on-treatment/end of treatment time points, as appropriate. Appropriate change from baseline measurements will be provided. For discrete measurement biomarkers, frequencies and percentages of categorical biomarker measures will be determined at baseline and on-treatment/post-treatment time points, as appropriate; shift tables may also be provided.

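### The secondary objective on correlating antitumor activity with baseline biomarkers is served, in the readable SAP, only by response and status categories, although continuous tumor shrinkage is already derived

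*SAP*

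**What the plan says.** Section 2.1 lists as a secondary objective: "To assess the correlation of antitumor activity of avelumab and other immune modulators with immune biomarkers in baseline tumor tissue". Section 3.2.5 names the endpoints: "Biomarkers such as PD-L1 expression and tumor infiltrating CD8+ T lymphocytes in baseline tumor tissue". Table 3 puts both on a percentage scale. CD8 is "The percent of counted cells that are scored as CD8"-positive, and PD-L1 is a percentage of counted cells together with a qualitative staining assessment.

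Section 6.2.5, the analysis section for these endpoints, begins "For continuous measurement biomarker results, summary statistics" and goes on to change from baseline, frequencies and shift tables. It contains no efficacy variable.

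Section 6.4 holds the two links to activity that can be read: ORR and DR by PD-L1 status (positive, negative, unknown), and the sentence "For CD8, descriptive statistics will be provided by objective response category". Section 5.2 sets the level of reporting: "Biomarker data will be summarized based on the biomarker analysis sets by treatment group as noted above".

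Section 6.2.2.1 separately derives a continuous measure of activity: "Tumor shrinkage will be summarized as the percent change from baseline in target lesions". It adds the maximum reduction per patient and a waterfall plot: "These plots will display the best percentage change from baseline in the sum of the diameters of all target lesions for each patient", restricted to patients with measurable disease at baseline and at least one post-baseline assessment.

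**The concern.** The objective asks for a correlation, and both sides of it exist as continuous variables, but no readable output puts them together. CD8 is compared between responders and non-responders, and PD-L1 enters only as a category. Everything that distinguishes a tumor that shrank by 25% from one that doubled is set aside, because both patients are non-responders.

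The cohorts are small, so the responder column for CD8 may hold only one or two values. A mean and SD from so few patients say almost nothing about association. At stake is whether a stated secondary objective gets an answer. No primary analysis, decision rule or error rate is affected.

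**Working it through.** **Inputs from the SAP.** Section 5.1.1 plans 20 patients each in A6, A7, A9 and A10, 20 PD-L1-positive patients in A8 and 20 in each of F1-F3. It plans 28 in each of A1-A4, 35 in A5, and 25 in each Phase 2 cohort of B, C and D. Section 2.2.1 reports that A7 enrolled 10. Section 5.1.2 gives at most 12 per Phase 1b dose level in B and D. The null response rates are 15% (A1-A4) and 20% (A5), with alternatives of 35% and 40%.

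**The plan's own figures.** The SAP gives no figure for the biomarker analysis. Its stated precision reproduces: √(0.25/20) = 0.112 and √(0.25/25) = 0.100. The rule of at least 8 of 28 gives one-sided alpha 0.049 and power 0.818.

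**Size of the responder column.** With X binomial (N, ORR), P(X ≤ 2) is the sum of the first three terms. For N=20 and ORR 10%: 0.9^20 + 20(0.1)(0.9^19) + 190(0.01)(0.9^18) = 0.122 + 0.270 + 0.285 = 0.677.

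| N | ORR 10% | ORR 15% | ORR 20% | ORR 35% |
|---|---|---|---|---|
| 10 | 0.93 | 0.82 | 0.68 | 0.26 |
| 20 | 0.68 | 0.41 | 0.21 | 0.01 |
| 25 | 0.54 | 0.25 | 0.10 | 0.002 |
| 28 | 0.46 | 0.19 | 0.06 | 0.001 |

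Very small responder groups are therefore common at or below the null rates and rare at the 35% alternative.

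**Information lost by splitting.** For a bivariate normal pair with a weak association, the efficiency of dichotomising activity at response rate p, relative to keeping it continuous, is φ(z_p)²/[p(1−p)]. This gives 0.34 at p=10%, 0.43 at 15%, 0.49 at 20% and 0.60 at 35%.

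**Illustrative detection rates.** The assumptions, none of them in the SAP, are a latent correlation of 0.5, responders being the patients with most shrinkage, and a two-sided 5% level. Unscanned patients are taken to be those with the least shrinkage, 20% or 30% of the cohort. Four analyses are compared over 4000 simulated cohorts per setting. Where a range is shown, it covers the two missing shares.

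| N, responders | Spearman, all scanned | Spearman, unscanned given worst rank | Spearman, unscanned dropped | Rank comparison by response |
|---|---|---|---|---|
| 20, 2 | 0.58 | 0.56-0.57 | 0.24-0.33 | 0.18 |
| 25, 3 | 0.67-0.68 | 0.65-0.66 | 0.28-0.39 | 0.27 |
| 28, 4 | 0.75 | 0.72-0.74 | 0.35-0.43 | 0.32-0.33 |
| 28, 10 | 0.74 | 0.71-0.73 | 0.34-0.42 | 0.51 |

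Separate runs agree with these to within about 0.02 (for N=25 with 3 responders, 0.65-0.69 for full or worst-rank data and 0.28-0.40 for dropped). The gain from continuous shrinkage depends on how unscanned patients are handled. Dropping the worst outcomes removes most of it, and at N=28 with 10 responders it does worse than the split.

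**Precision of one cohort.** The Fisher interval for an observed r=0.5 at N=20 is tanh(0.549 ± 1.96/√17) = tanh(0.549 ± 0.475), that is 0.07 to 0.77. At N=25 it is 0.13 to 0.75.

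**The case against.** The strongest reply is that the plan is deliberately descriptive. The version history records that Section 6.2.5 was simplified to descriptive summaries and that the PD-L1 subset and the CD8 table were added later. Confirmed objective response is the trial's primary activity measure, and both named biomarkers are related to it. The plan contains no test for CD8, so the detection rates above are not its power. This stands. The rates serve only as a gauge of how much information each display carries.

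The second reply is that shrinkage is missing for patients without measurable disease or a post-baseline scan, whereas Section 6.1.2.1 keeps early failures in as non-responders. This also stands. A complete-case correlation could be no better than the planned table, which is why the handling of these patients belongs in the fix.

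Third, few responders is not a given. Tables 4 to 6 run up to 15 of 20 and 20 of 25, and at the 35% alternative the responder column is adequate. But Sections 2.2.1 to 2.2.3 report insufficient activity in several cohorts, and the loss from splitting persists at 35%.

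A reader might infer that no correlation is planned anywhere, or that the objective is abandoned. The documents do not support that. Section 6.3 and part of the endpoint list are redacted, and Section 6.4 does relate each biomarker to response. Nor does the CD8 sentence itself say that it applies within each treatment group. That reading comes from Section 5.2 and the lead-in to Section 6.4.

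**Conclusion.** The point holds as a mismatch between a stated objective and the readable analysis. The objective says correlation, Section 6.2.5 links no biomarker to activity, and Section 6.4 links them only through categories, although continuous shrinkage is at hand. Under the assumed correlation of 0.5, with 25 patients and 3 responders, the better analysis detects the association about 65-69% of the time against about 27%. That advantage holds only if early failures without a scan are kept at the worst rank, and the simulation assumes that they truly are the worst outcomes.

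It would be too much to say that the plan cannot address the objective, or that a correlation would settle it. A single cohort stays imprecise under either approach. Severity is minor: one secondary, descriptive objective.

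**What to change.** In Sections 6.2.5 and 6.4, for each treatment group with at least 10 evaluable patients, add a scatter plot and a Spearman correlation with 95% CI of baseline CD8 percent, and of baseline PD-L1 percent, against best percent change in target lesions as derived in Section 6.2.2.1. Mark points by confirmed objective response.

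- Give the worst rank to patients with measurable disease who have no post-baseline scan because of early progression or death.
- Repeat on complete cases as a sensitivity analysis, and show how many patients are omitted and why.
- Keep the planned CD8 table by response category and the PD-L1 subsets.
- Label the analysis as exploratory estimation, without multiplicity control.
- A pooled estimate stratified by cohort is optional, since combinations, doses and tumor types differ.

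The cost is two more displays from variables already defined, and one convention for unscanned patients. Patients without measurable disease remain outside the correlation.

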## **6.5. Baseline and Other Summaries and Analyses**

### **6.5.1. Baseline summaries**

#### **Combinations A and F**

The following analyses will be based on the FAS overall and separately by treatment group using the data from the combined Phases 1b and 2 (Cohorts A1, A2, A3 and Cohorts F1, F2, F3) and the data from Phase 2 (Cohorts A4, A5, A6, A7, A8, A9, A10).

#### **Combinations B, C and D**

The following analyses will be based on the FAS overall and separately by treatment group using the data from Phase 1b and from Phase 2 separately and for each combination.

##### **6.5.1.1. Demographic characteristics**

Demographic characteristics will be summarized by treatment group using the following information from the 'Screening/Baseline Visit' eCRF pages.

- Demographic characteristics
  - Gender: Male, Female
  - Race: White, Black or African American, Asian, American Indian or Alaska Native, Native Hawaiian or Other Pacific Islander, Other, Unknown
  - Ethnic origin:
    - Hispanic or Latino
    - Not Hispanic or Latino
  - Age (years): summary statistics
  - Age categories:
    - < 65 years, ≥ 65 years

- < 65, 65-<75, 75-<85, ≥ 85 years
- Pooled Geographical Region (as applicable):
  - North America
  - Europe
  - Asia
  - Rest of the World (Australasia, Latin America, Africa and/or Middle East will be included as additional pooled geographical regions if including > 10% of the overall randomized/treated population)
- Geographic Region (as applicable):
  - North America
  - Latin America
  - Western Europe
  - Eastern Europe
  - Middle East
  - Australasia
  - Asia
  - Africa
- Eastern Cooperative Oncology Group (ECOG) Performance Status: 0, 1, 2, 3, and 4
- Baseline disease status
  - HPV status (positive, negative) for SCCHN patients

Center codes will be used for the determination of the patient's geographic region.

The listing of demographics and baseline characteristics will include the following information: patient identifier, treatment group, age, sex, race, ethnicity, and ECOG performance status.

#### **6.5.1.2. Medical history**

Medical history will be coded using the most current available version of Medical Dictionary for Regulatory Activities (MedDRA) and will be summarized from the 'Medical History' eCRF page. Medical history will be summarized as the numbers and percentages of patients by MedDRA preferred term (PT) as event category and MedDRA primary system organ class (SOC) as summary category. Each patient will be counted only once within each PT or SOC.

Medical history will be displayed in terms of frequency tables: ordered by primary SOC and PT in alphabetical order.

### 6.5.1.3. Disease characteristics

Information on disease characteristics collected on ‘Primary Diagnosis’ and RECIST eCRF pages will be summarized overall and by treatment group. Summary statistics will be presented for the following.

From the ‘Primary Diagnosis’ eCRF page:

- Site of primary tumor
- Primary diagnosis (summarize all categories collected in the ‘Primary Diagnosis’ eCRF page)
- Time since initial diagnosis to ‘start date’ (months), defined as (‘start date’ – date of initial diagnosis)/30.4375
- Time since diagnosis of local/regional recurrence of disease (months), defined as (‘start date’ – date of diagnosis of local/regional recurrence of disease)/30.4375

From the RECIST eCRF page:

- Measurable disease (lesions) at baseline (Yes, No)
- Involved tumor sites at baseline

Listing of disease history will be provided with all relevant data (as collected on the ‘Primary Diagnosis’ eCRF pages) and derived variables as above.

### 6.5.1.4. Prior anti-Cancer therapies

The prior anti-cancer therapies are collected under the ‘Prior Cancer Therapy’, ‘Prior Radiation Therapy’ and ‘Prior Surgery’ eCRF pages.

The number and percentage of patients in each of the following anti-cancer therapy categories will be tabulated:

- Patients with at least one type of prior anti-cancer treatment
- Patients with at least one prior anti-cancer drug therapy
- Patients with at least one prior anti-cancer radiotherapy
- Patients with at least one prior anti-cancer surgery

Prior anti-cancer drug therapy will be summarized as follows based on the number and percentage of patients with the following:

- At least one prior anti-cancer drug therapy
- Number of prior anti-cancer drug therapy regimens: missing, 1, 2, 3,  $\geq 4$  for metastatic disease

- Prior anti-cancer immune therapy (including PD-1, PD-L1, anti-CTLA4, others)
- Intent of Drug Therapy: Neo-Adjuvant, Adjuvant, Advanced / Metastatic, Locoregional disease /Recurrence
- Best response: CR, PR, SD, PD, Unknown, Not applicable. Best response is derived from the last treatment regimen.

The prior anti-cancer drug therapies will also be summarized based on the number and percentage of patients by the drug class and preferred term. A patient will be counted only once within a given drug class and within a given drug name, even if he/she received the same medication at different times. The summary will be sorted on decreasing frequency of drug class and decreasing frequency of drug name in a given drug class. In case of equal frequency regarding drug class (respectively drug name), alphabetical order will be used.

Prior anti-cancer drug therapies will be included in the listings that follow with a flag to identify prior therapies. These will include the patient identification number, and all the relevant collected data-fields on the corresponding eCRF pages.

- Listing of anti-cancer drug therapies

## **6.5.2. Study conduct and patient disposition**

### **Combinations A and F**

The following analyses will be performed based on the FAS overall and separately by treatment group using the data from the combined Phases 1b and 2 (Cohorts A1, A2, A3 and Cohorts F1, F2, F3) and the data from Phase 2 (Cohorts A4, A5, A6, A7, A8, A9, A10).

### **Combination B, C and D**

The following analyses will be performed based on the FAS overall and separately by treatment group using the data from Phase 1b and Phase 2 separately and for each combination.

#### **6.5.2.1. Patient disposition**

*For randomized cohorts*

The percentages below will be calculated based on the number of patients in the FAS.

- Total number of patients screened overall
- Number of patients who discontinued from the study prior to randomization overall and by the main reason for discontinuation
- Number and percentage of randomized patients in each of the analysis sets defined in Section 4
- Number and percentage of randomized patients with study drug ongoing (separately for each study drug when administered in combination)

- Number and percentage of randomized patients who discontinued study drug overall and by the main reason for discontinuation of study drug (separately for each study drug when administered in combination)
- Number and percentage of patients who entered follow-up
- Number and percentage of patients who discontinued follow-up overall and by the main reason for discontinuation
- Number and percentage of patients who entered long-term follow-up
- Number and percentage of patients who discontinued long-term follow-up overall and by the main reason for discontinuation

The results of the randomization algorithm will be summarized as follows:

- Number and percentage of randomized patients overall, by region (Europe, EEA (required by EudraCT), North America, Latin America, Middle East, Asia, Australasia, Africa), by country within region
- Number and percentage of randomized patients by center
- Cross tabulation: patients randomized vs. patients treated (Cohorts A1, A2 and A3, Cohorts A9 and A10, and Cohorts F1, F2 and F3)

*For non-randomized cohorts*

The percentages below will be calculated based on the number of patients in the FAS.

- Total number of patients screened overall
- Number of patients who discontinued from the study prior to treatment with study drug overall and by the main reason for discontinuation
- Number and percentage of treated patients in each of the analysis sets defined in Section 4
- Number and percentage of patients with study drug ongoing (separately for each study drug when administered in combination)
- Number and percentage of patients who discontinued study drug overall and by the main reason for discontinuation of study drug (separately for each study drug when administered in combination)
- Number and percentage of patients who entered follow-up
- Number and percentage of patients who discontinued follow-up overall and by the main reason for discontinuation
- Number and percentage of patients who entered long-term follow-up

- Number and percentage of patients who discontinued long-term follow-up overall and by the main reason for discontinuation

In addition, the following will be summarized:

- Number and percentage of treated patients overall, by region (Europe, EEA (required by EudraCT), North America, Latin America, Middle East, Asia, Australasia, Africa), by country within region
- Number and percentage of treated patients by center

